3.7. Data Handling Conventions and Transformations

Where appropriate, safety data for subjects that did not complete the study will be included in summary statistics.

- If a subject received study drug, the subject will be included in the summary of AEs according to the treatment received; otherwise, if the subject is not dosed then they will be excluded from the summary.

Laboratory data that are continuous in nature but are less than the lower limit of quantitation (LLOQ) or above the upper LOQ will be imputed as follows:

- A value that is 1 unit less than the lower LOQ will be used for calculation of descriptive statistics if the data is reported in the form of “<x” (x is considered the LOQ). For example, if the values are reported as <50 and <5.0, then values of 49 and 4.9 will be used for calculation of summary statistics, respectively.
- A value that is 1 unit above the upper LOQ will be used for calculation of descriptive statistics if the data is reported in the form of “>x” (x is considered the LOQ). For example, if the values are reported as >50 and >5.0, then values of 51 and 5.1 will be used for calculation of summary statistics, respectively.
- The LOQ will be used for calculation of descriptive statistics if the data is reported in the form of “≤ x” or “≥ x” (x is considered as the LOQ).

PK concentration values that are below the limit of quantitation (BLQ) will be presented as “BLQ” in the concentration data listing. Values that are BLQ will be treated as 0 at pre-dose time points, and one-half the value of the LLOQ at post-baseline time points, where LLOQ is corrected for the dilution factor (ie, reported LLOQ/dilution factor) for determination of summary and order statistics.

The following conventions will be used for the presentation of summary and order statistics:

- If at least 1 subject has a concentration value of BLQ for the time point, the minimum value will be displayed as “BLQ”
- If more than 25% of the subjects have a concentration value of BLQ for a given time point, the minimum and Q1 values will be displayed as “BLQ”
- If more than 50% of the subjects have a concentration value of BLQ for a given time point, the minimum, Q1, and median values will be displayed as “BLQ”
- If more than 75% of the subjects have a concentration value of BLQ for a given time point, the minimum, Q1, median, and Q3 values will be displayed as “BLQ”
- If all subjects have concentration values of BLQ for a given time point, all order statistics (minimum, Q1, median, Q3, and maximum) will be displayed as “BLQ”

PK parameters that are BLQ will be imputed as one-half LLOQ before log transformation or statistical model fitting.

3.8. Analysis Visit Windows

3.8.1. Definition of Study Day

Study day is the day relative to the randomization date. Study Day 1 is defined as the randomization day.

Study day will be calculated from the date of randomization and defined as:

- Post-randomization: (assessment date) – (date of Study Day 1) + 1
- Prior to randomization: (assessment date) – (date of Study Day 1).

3.8.2. Analysis Visit Windows

Subject visits might not occur on protocol-specified days. Therefore, for the purpose of analysis, observations will be assigned to analysis windows.

The analysis windows are provided in [Table 1](#).

Table 1 Analysis Visit Windows for Double Blind Phase for All Except ECG

Nominal Visit	Analysis Visit	Nominal Day	Lower Limit	Upper Limit
Baseline	Baseline	1	n/a	1
Week 2	Week 2	14	2	21
Week 4	Week 4	28	22	42
Week 8	Week 8	56	43	70
Week 12	Week 12	84	71	98

Nominal Visit	Analysis Visit	Nominal Day	Lower Limit	Upper Limit
Week 16	Week 16	112	99	126
Week 20	Week 20	140	127	154
Week 24	Week 24	168	155	189
Week 30	Week 30	210	190	231
Week 36	Week 36	252	232	273
Week 42	Week 42	294	274	315
Week 48	Week 48	336	316	343

Table 2. Analysis Visit Windows for Double-Blind Phase ECG Only

Nominal Visit	Analysis Visit	Nominal Day	Lower Limit	Upper Limit
Baseline	Baseline	1	n/a	1
Week 24	Week 24	168	2	252
Week 48	Week 48	336	253	420

Vital signs, weight, ECG and safety laboratory data collected after last dose date of any study drug will be summarized up to last dose date plus 30 days, and labeled as “FU-30 Day”. For any subjects on ENTO from baseline to Week 48 who decided to enroll into the OLE phase, there will not be a 30 day follow up visit. An unscheduled visit prior to the first dosing of study drug may be included in the calculation of the baseline value, if applicable. The nominal day of “FU-30 Day” is the last dose date plus 30 days. The lower limit of window for “FU-30 Day” is the upper limit of last on drug visit window plus 1, while the upper limit is Follow-Up Day 30.

Follow-Up Day 1 is the date of the last dose of study drug plus 1.

Nominal Visit	Analysis Visit	Nominal Follow-Up Day	Lower Limit in Follow-Up Day	Upper Limit in Follow-Up Day
FU-30 Day	FU-30 Day	30	1	30

3.8.3. Selection of Data in the Event of Multiple Records in an Analysis Visit Window

Depending on the statistical analysis method, single values may be required for each analysis window. For example, change from baseline by visit usually requires a single value, whereas a time-to-event analysis would not require 1 value per analysis window.

If multiple valid, nonmissing, continuous measurements exist in an analysis window, records will be chosen based on the following rules if a single value is needed:

- In general, the baseline value will be the last nonmissing value on or prior to the first dose date of study drug, unless otherwise specified. If multiple measurements occur on the same day, the last nonmissing value prior to the time of first dose of study drug will be considered as the baseline value. If these multiple measurements occur at the same time or the time is not available, the average of these measurements (for continuous data) will be considered the baseline value.
- For postbaseline visits:
 - The record closest to the nominal day for that visit will be selected.
 - If there are 2 records that are equidistant from the nominal day, the later record will be selected.
 - If there is more than 1 record on the selected day, the average will be taken, unless otherwise specified.

If multiple valid, nonmissing, categorical measurements exist in an analysis window, records will be chosen based on the following rules if a single value is needed:

- For baseline, the last available record on or prior to the date of the first dose of study drug will be selected. If there are multiple records with the same time or no time recorded on the same day, the value with the lowest severity will be selected (eg, normal will be selected over abnormal for safety ECG findings).
- For postbaseline visits:
 - The record closest to the nominal day for that visit will be selected.
 - If there are 2 records that are equidistant from the nominal day, the later record will be selected.
 - If there is more than 1 record on the selected day, the value with the worst severity will be taken (eg, abnormal will be selected over normal for safety ECG findings), unless otherwise specified.

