6.5.2. Early Study Drug Discontinuation (ESDD)

If the subject discontinues study drug prior to the end of study, the subject will be asked to return to the clinic within 72 hours of stopping study drug for the Early Study Drug Discontinuation Visit. The subject will be asked to continue attending the schedule study visits through Week 48. Subjects who ESDD will not be eligible for the OLE phase of the study.

At the ESDD visit, any evaluations showing abnormal results indicating that there is a possible or probable causal relationship with the study drug, should be repeated weekly (or as often as deemed prudent by the investigator) until the abnormality is resolved, returns to baseline, or is otherwise explained.

Evaluation listed in [Table 6-1](#) will be completed at the ESDD visit.

The following will be conducted at the ESDD: review of adverse events (AEs) and changes in concomitant medications, vital signs (including weight), complete physical exam, primary malignancy assessment (if applicable), blood for hematology, chemistry, metabolic panel, selected biomarkers and urine for: pregnancy test (if applicable), and urinalysis. The NCAA and LSS will be assessed.

PFTs will be required at ESDD: spirometry with bronchodilator and diffusing capacity of the lungs for carbon monoxide (DLCO).

6.6. 30 Day Follow-Up Visit

Subjects who complete through Week 48 visit and who do not wish to participate in the OLE phase of the study will return to the clinic 30 days after the completion of study drug for the 30-Day follow-up visit. Subjects who complete the OLE will return to the clinic 30 days after the completion of study drug for the 30-Day follow-up visit

Subjects who permanently discontinue study drug and refuse to continue in the study will be asked to return to the clinic 30 days after the completion of the ESDD visit for the 30-Day follow-up visit.

For the purpose of scheduling a 30-Day follow-up visit, a ± 5 days window may be used. [Table 6-1](#) lists all procedures to be completed at the 30-Day Follow-up visit.

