7.2.2.1. Treatment-Emergent Laboratory Abnormalities

Double blind phase treatment-emergent laboratory abnormalities are defined as values that increase at least 1 toxicity grade from baseline at any post-baseline time point, up to and including the earlier of the date of last dose of study drug plus 30 days, or the first dose of OLE study drug if any.

OLE phase treatment-emergent laboratory abnormalities are defined as values that increase at least 1 toxicity grade from OLE day 1 (first OLE dose date) at any post-OLE day 1 time point, up to and including the date of last dose of OLE study drug plus 30 days.

If the relevant baseline laboratory value is missing, any abnormality of at least Grade 1 observed within the time frame specified above will be considered treatment emergent.

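### The SAP closes the FU-30 Day window at Follow-Up Day 30, but the protocol allows that visit up to Day 35 (Day 38 for some early stoppers), so some compliant visits miss the by-visit safety tables

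*SAP*

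**What the plan says.** **SAP 3.8.2.** Vital signs, weight, ECG and safety laboratory data taken after the last dose are summarized up to last dose plus 30 days and labelled FU-30 Day. The counting origin is explicit: "Follow-Up Day 1 is the date of the last dose of study drug plus 1". The table row reads "FU-30 Day FU-30 Day 30 1 30", that is, nominal day 30, lower limit 1, upper limit 30. The text above the table says that the lower limit "is the upper limit of last on drug visit window plus 1, while the upper limit is Follow-Up Day 30". It thus gives the same upper limit but starts the window after the last on-drug visit window has closed.

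**SAP 3.8.3.** When several post-baseline records fall in one window: "The record closest to the nominal day for that visit will be selected".

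**SAP 3.1.2 and 7.2.2.1.** Safety summaries stop at last dose plus 30 days, or at the first open-label extension (OLE) dose if that is earlier. Treatment-emergent laboratory abnormalities count "up to and including the earlier of the date of last dose of study drug plus 30 days" or the first OLE dose. Protocol 8.2.1.2 and 8.6 use the same 30-day cut.

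**Protocol 6.6.** Completers who do not enter the OLE return 30 days after finishing study drug. Subjects who permanently stop drug and refuse to continue "return to the clinic 30 days after the completion of the ESDD visit". On timing: "For the purpose of scheduling a 30-Day follow-up visit, a ± 5 days window may be used". Protocol Table 6-1, footnote d, places the ESDD visit within 72 hours of the last dose.

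**The concern.** Visit windows exist to absorb visits that do not land on the planned day. This one has room for an early visit but none for a late one, because its upper limit is also its nominal day. The protocol allows lateness at exactly this visit. For some early stoppers it makes lateness the plan: if ESDD is one to three days after the last dose, the target for the follow-up visit is already past Day 30.

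Two faults in the tables follow. A visit done on schedule can be missing from its own row. An end-of-treatment sample can also stand in that row under a label that tells the reader it is a 30-day value.

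The study was stopped, and SAP 2.3 holds the final analysis until every subject has had the follow-up or early-termination visit. The plan waits for these visits and then leaves some of them out of the summaries. Separately, the two lower limits in SAP 3.8.2 would let two programmers build different tables from the same data.

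**Working it through.** This is date arithmetic; no error-rate or sample-size formula applies.

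**1. The SAP's own limit.** Follow-Up Day k is last dose + k, so last dose + 30 is Follow-Up Day 30. This reproduces the table's nominal day and upper limit, and matches the cut in SAP 3.1.2.

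**2. Permitted visit days.** Day = ESDD offset d + 30, ±5. For completers d = 0. For early stoppers who leave the study d runs from 0 to 3 (72 hours).

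| d | Target day | Permitted days | Days after 30 |
|---|---|---|---|
| 0 (also completers) | 30 | 25–35 | 5 of 11 |
| 1 | 31 | 26–36 | 6 of 11 |
| 2 | 32 | 27–37 | 7 of 11 |
| 3 | 33 | 28–38 | 8 of 11 |

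The latest permitted day is 3 + 30 + 5 = 38. An upper limit of 35 would cover completers; 38 is needed for everyone.

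**3. Which record fills the row.** Take a subject with samples on Follow-Up Days 3 (ESDD) and 33 (30-Day visit) and nothing else after the last dose.
- Upper limit 30, table lower limit 1: only day 3 is eligible, so day 3 is reported as FU-30 Day.
- Upper limit 38: distances from day 30 are |3 − 30| = 27 and |33 − 30| = 3, so day 33 is reported.

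If the visit had been on day 28, it would be chosen under either limit. The substitution needs a follow-up visit on day 31 or later and no other record nearer day 30 within the window.

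**4. The two lower limits.** The table and the labelling sentence start at Follow-Up Day 1. The text starts at the upper limit of the last on-drug window plus 1. For a last dose on day 168, the Week 24 window ends at day 189, so the text limit is 189 + 1 − 168 = Follow-Up Day 22. At the nominal days of the scheduled visits this limit is Follow-Up Day 8 (Weeks 2 and 48), 15 (Weeks 4–20) or 22 (Weeks 24–42). Under the text rule a day-3 ESDD sample would in these cases fall outside FU-30 Day. The mislabelling in step 3 therefore comes from the table and the labelling sentence, not from the text limit.

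**The case against.** **The 30-day cut is the protocol's own.** Protocol 8.2.1.2, 8.6 and 8.6.2 end safety summaries and treatment-emergent adverse events 30 days after the last dose, and the SAP follows them. This stands. The conflict between visit window and data cut starts in the protocol, and changing the treatment-emergent laboratory cut in the SAP alone would break the match with adverse events.

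**Nothing is lost from the record.** Late laboratory data are listed (protocol 8.6.3, SAP 7.2). The Grade 3 or 4 listing in SAP 7.2.2.3 covers all results collected in the study for the test concerned. This stands: the loss is from summary tables only.

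**The SAP may label its row as it likes.** FU-30 Day is defined to include everything after the last dose up to day 30, so an ESDD sample belongs there by definition. This is true of the rule, but the row's nominal day is 30, and a reader will not take a day-3 value for what it is.

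**A reader might infer that the window is often empty.** If the text limit is applied to the window that contains the last-dose day, the lower limit exceeds Follow-Up Day 30 for 41 of 342 last-dose days (5 in the Week 24 window and 12 each in Weeks 30, 36 and 42). But the SAP speaks of the last on-drug *visit* window. The affected last-dose days (155–159, 190–201, 232–243, 274–285) all precede the earliest permitted visit in their window (days 165, 205, 247 and 289). An empty window would need an unscheduled or ESDD visit in those days. Nor can it occur under the table limits, which are what allow the ESDD substitution.

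**A reader might infer that a liver signal would be missed.** The two transaminase events in protocol 1.2.2 do not support that. One began 7 days after the last dose. The other followed symptoms one day after the last dose and peaked a week later. Both lie well inside 30 days. Protocol 6.5.2 also asks for abnormal ESDD results with a possible or probable link to study drug to be repeated weekly or as often as judged prudent. Such repeats would fall in the existing window and displace the ESDD value.

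**Conclusion.** The point holds as a conflict between the SAP's analysis window and the protocol's visit schedule, plus a contradiction within SAP 3.8.2 on the lower limit. Compliant 30-Day visits on days 31–35 for completers, and on days 31–38 for early stoppers who leave the study, are left out of the by-visit laboratory and vital-sign summaries. Under the table limits an ESDD value can take their place.

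The size cannot be fixed from the documents. It is tempting to read 5 of 11 permitted days (45%) as the share of completers' visits lost. That would require every permitted day to be equally likely, whereas visits are aimed at day 30, which is inside the window for completers. Day 38 applies only to subjects who stop early and refuse to continue; other early stoppers are asked to attend scheduled visits through Week 48 (protocol 6.5.2).

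The consequence is limited to descriptive safety tables in a study already stopped for lack of efficacy. The primary endpoint is untouched. Nothing here shows that the +30-day treatment-emergent definitions are wrong.

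**What to change.** In SAP 3.8.2:
- Assign the actual protocol 30-Day Follow-up visit to FU-30 Day if it falls by Follow-Up Day 38 and before any OLE dose.
- Give ESDD samples their own label so that they cannot fill that row.
- Keep a single lower limit. Deleting the text clause and keeping the table's Day 1 is the simplest course once ESDD is labelled separately. The documents give no basis for a later cut-off.

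In SAP 3.1.2, state that this by-visit row is an exception to the last dose + 30 days cut. Record the exception in SAP 7.7, which now declares no deviation from the protocol's safety analyses.

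Leave the +30-day treatment-emergent definitions for adverse events (SAP 7.1.5.1) and laboratory abnormalities (SAP 7.2.2.1 and 7.2.2.2) unchanged, unless the protocol is amended with them.

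The cost is SAP wording and a small programming change, with no new data. The drawback is that a few by-visit values will lie up to 38 − 30 = 8 days beyond the treatment-emergent cut; a table footnote can say so.

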4. SUBJECT DISPOSITION

4.1. Subject Enrollment and Disposition

A summary of subject enrollment will be provided by treatment group for each country, investigator and overall. The summary will present the number and percentage of subjects enrolled. For each column, the denominator for the percentage calculation will be the total number of subjects analyzed for that column.

A similar enrollment table will be provided by randomization stratum. The denominator for the percentage of subjects in the stratum will be the total number of enrolled subjects within that stratum. If there are discrepancies in the value used for stratification assignment between the IWRS and the clinical database, the value collected in the clinical database will be used for the summary. A listing of subjects with discrepancies in the value used for stratification assignment between the IWRS and the clinical database at the time of data finalization will be provided.

A listing of subject enrollment will be provided to describe site, subject number, subject stratification, informed consent date, first screening date, and randomization date.

A summary of subject disposition will be provided by treatment group and overall. This summary will present:

- Number of subjects screened
- Number of subjects randomized (ITT Analysis Set)
- Number and percentage of subjects randomized and treated with study drug (Safety Analysis Set)
- Number and percentage of randomized subjects in the PK Analysis Sets
- Number and percentage of randomized subjects who discontinued study drug, and the reasons for study drug discontinuation
- Number and percentage of randomized subjects who discontinued from the study, and the reasons for study discontinuation

No inferential statistics will be generated.

A listing of subject disposition for all randomized subjects will be generated to describe subject number, randomized study drug (ENTO or placebo) assignment, actual study drug assignment, first dose date, last dose date, duration of study drug treatment, reason for study drug and study discontinuation. A separate listing of reasons for screen failure will be provided by screening ID number in ascending order.

4.2. Extent of Study Drug Exposure and Adherence

Extent of exposure to study drug will be examined by assessing the total duration of exposure to study drug and the level of adherence to the study drug specified in the protocol.

4.2.1. Duration of Exposure to Study Drug

Duration of exposure is defined as (last dose date – first dose date + 1), regardless of temporary interruptions in study drug administration, and will be expressed in weeks (recorded to 1 decimal place, eg, 4.5 weeks).

Duration of exposure to study drug will be summarized using descriptive statistics (n, mean, SD, median, Q1, Q3, minimum, and maximum) and as the number and percentage of subjects exposed for at least 4, 8, 12, 24, 36 and 48 weeks.

Summaries will be provided by treatment group for the Safety Analysis Set. No inferential statistics will be provided.

4.2.2. Adherence to Study Drug

A separate by-subject listing of study drug administration and drug accountability will be provided by subject ID number (in ascending order) and visit (in chronological order).

Adherence will be determined by the reporting of doses taken as documented on the study drug administration eCRF.

Adherence to study drug (%) is defined as (total days on drug) / [Last dose date – First dose date + 1]. Subjects are defined as treatment compliant if they achieved at least 80% adherence. The total number of doses administered will also be summarized.

Descriptive statistics for adherence and total number of doses taken (n, mean, SD, median, Q1, Q3, minimum, and maximum) along with the number and percentage of subjects belonging to adherence categories (eg, < 80%, ≥ 80%) will be provided by treatment group for the Safety Analysis Set. Adherence will also be listed.

4.3. Protocol Deviations

Subjects who did not meet the eligibility criteria for study entry, but enrolled in the study will be summarized regardless of whether they were exempted by the sponsor or not. The summary will present the number and percentage of subjects who did not meet at least 1 eligibility criterion and the number of subjects who did not meet specific criteria by treatment group based on all enrolled subjects. A by-subject listing will be provided for those subjects who did not meet at least 1 eligibility (inclusion or exclusion) criterion. The listing will present the eligibility criterion (or criteria if more than 1 deviation) that subjects did not meet and related comments, if collected.

Protocol deviations occurring after subjects entered the study are documented during routine monitoring. The number and percentage of subjects with important protocol deviations by deviation reason will be summarized by treatment group for the ITT Analysis Set. A by-subject listing will be provided for those subjects with any protocol deviation.

5. BASELINE CHARACTERISTICS

5.1. Demographics

Subject demographic variables (ie, age, sex, race, ethnicity and region) will be summarized by treatment group and overall using descriptive statistics for age, and using number and percentage of subjects for sex, race, ethnicity and region. Age at baseline is calculated in years at randomization date was made. The summary of demographic data will be provided for the ITT Analysis Set.

